### **2.3.2 Study duration per subject**

For each subject, the first 3 periods of the study will last a maximum of 66 weeks, as follows:

- Up to 6 weeks in the Screening period
- 52 weeks in the double-blind period
- A Follow-up visit, 8 weeks after Week 52/WD visit for subjects not participating in the SFE Period.

For subjects participating in the SFE period, the study will extend up to a maximum of 104 additional weeks.

The end of the study will be defined as the date of the last subject's last visit, defined as the Follow-up Visit 8 weeks after Week 52/WD visit for subjects not participating in the SFE Period, or the last visit of the SFE Period (Week 156/SFE-WD).

### **2.3.3 End of periods and study**

The end of the study is defined as the date of the last visit (including Follow-up visit and SFE period) of the last subject in the study. Period start and ends are defined in [Section 3.2.1](#).

### **2.3.4 Planned number of subjects and sites**

Approximately 1200 subjects are expected to enter the Screening period in order to have 300 subjects randomized into the double-blind period. It is planned to enroll the subjects at approximately 120 sites.

### **2.3.5 Anticipated regions and countries**

The study will be conducted in North America, Australia, Europe, Asia, and other regions as appropriate.

### **2.3.6 Stratification**

Randomization will be stratified on:

- Region
  - North America: Canada and USA
  - Europe: Bulgaria, Czech Republic, Hungary, Poland and Russia
  - Asia: Australia, and Taiwan
- MRI/CRP classification

Subjects will be classified as MRI+/- depending on whether or not they have evidence of sacroiliitis on MRI at Screening based on the ASAS/OMERACT definition. Subjects will be classified as CRP+/- based on the CRP value obtained at the second Screening visit scheduled to occur 3 to 5 days prior to Baseline. Subjects will be categorized as CRP+ if their CRP value is above the level indicative of inflammatory disease at this visit. Otherwise, they will be considered CRP-. Based on these definitions, the stratification for MRI/CRP classification will have the following 3 levels:

- MRI+/CRP+
- MRI+/CRP-
- MRI-/CRP+

Subjects who are MRI-/CRP- are not eligible for randomization. The interactive response system (IXRS) will be designed to ensure that at least 20% of the randomized subjects belong to one of the three clinical subgroups above.

## **2.4 Determination of sample size**

Subjects will be randomized in a 1:1 ratio to the CZP 200mg Q2W and placebo treatment groups. The expected response rates for ASDAS-MI at Week 52 are 40% and 20% for CZP and placebo, respectively. A total sample size of 300 (150 subjects per treatment group) provides 95% power to detect a statistically significant difference in the ASDAS-MI response rate at Week 52 between CZP and placebo based on a 2-sided significance level of 0.05.

## **3 DATA ANALYSIS CONSIDERATIONS**

### **3.1 General presentation of summaries and analyses**

All statistical analyses will be performed using SAS® (STATISTICAL ANALYSIS SYSTEM, SAS-Institute, Cary, NC, USA) according to UCB SOPs.

For continuous data in general, summary statistics (n [number of available measurements], arithmetic mean, SD, median, minimum, and maximum) will be presented by treatment group. For selected variables, the first (25th percent) quartile (Q1) and the third (75th percent) quartile (Q3) may also be presented (for patient reported outcomes).

Mean, SD, median and quartiles will be displayed to 1 more decimal place than collected in the source data. Derived variables in general will display the mean, SD and median to 1 more decimal place than the variables used in the derivation (i.e. a change from Baseline will be reported to the same precision as the Baseline data). However, a special rule can be defined as needed for appropriate reporting.

For descriptive statistics of continuous variables by visit, the change from Baseline and actual value at the given time point will be displayed. The change from Baseline is the post-Baseline value minus the Baseline value. If the Baseline or post-Baseline value is missing, then the change from Baseline is set to missing. Percent change from Baseline is the change from Baseline divided by Baseline and multiplied by 100. If the Baseline value is 0 and the post-Baseline value is also 0, then the percent change from Baseline is set to 0. If the Baseline value is 0 and the post-Baseline value is non-zero, then the percent change from Baseline is set to missing. If the Baseline value is missing, the percent change from Baseline is set to missing.

Frequency tables (frequency counts and percentages) will be presented for categorical data. If there are no missing values then the missing row can be removed. If there are missing values (including missing a single assessment or entire visit), then include the missing row with the frequency count and percentage. If there are no subjects in a specific electronic case report form (eCRF) category, then that row will be retained and 0 presented in the table.

In general, percentages will be calculated based on the utilized analysis set. However, in the case of subgroup analyses, the N of the subgroup will be used as denominator.

Unless stated otherwise, all inferential statistical tests will be 2-sided and conducted at the 0.05 alpha level. P-values will be presented to 3 decimal places. Relevant SAS output will be included in the 'Documentation of Statistical Methods' section of the CSR. All data in the database (SDTM and ADaM) will be presented in by-subject data listings, and sorted by treatment group, site, subject number, and visit (where applicable).

A fixed-sequence testing procedure will be used to control the overall Type 1 error for comparison of multiple efficacy endpoints. This procedure is described in [Section 8](#).

## **3.2 General study level definitions**

### **3.2.1 Analysis time points**

#### **3.2.1.1 Pre-treatment period**

The pre-treatment period (Screening period) of the study is the period prior to a subject's first dose of study medication administration. This period starts at the Screening visit (week -6 to -1 day) and ends at the Baseline visit (Week 0) up to the time of first study medication administration (exclusive). Unless specific time information is available to indicate that a Screening or Baseline visit assessment was performed after a subject's first study medication administration, all assessments will be attributed to the Screening period.

### 3.2.1.2 Double-blind treatment period

The double-blind treatment period begins at the Baseline visit (Week 0) at the time of first study medication administration (inclusive) and ends when:

- the subject takes their first dose of open-label CZP (OL-CZP) or open-label other treatment (OL-OT) for those who continue into the SFE or who switch to OL-CZP or OL-OT
- the later of Week 52 visit and last administration of double-blind treatment, for subjects who complete the 52 week main phase of the study and do not continue into the SFE and who do not switch to OL-CZP or OL-OT
- the subject discontinues the study on double-blind treatment prior to the week 52 visit (WD visit) and does not fall into the above categories.

For subjects who prematurely withdraw from the study prior to Week 52 (for example, those who cease to have double-blind and open-label visit data collected), their visit assessments at withdrawal will be assigned to the next scheduled visit following the last visit where assessments are available according to each protocol activity. This could be the next double-blind or open-label visit. All visit measurements, even violating the visit window, will be utilized for the respective visit as long as they are in the proper sequence.

Subjects will be classified as completing the main phase of the study if they complete the Week 52 visit without early withdrawal during the main phase of the study. This is regardless of whether they attend the Follow-up visit or enter SFE period and regardless of whether they are on double-blind treatment, OL-CZP, or OL-OT.

### 3.2.1.3 Open-label period

The open-label period starts when subjects have discontinued the double-blind treatment period prior to start of the SFE period and take their first dose of open-label CZP or other treatment. The open-label period ends when:

- the subject takes their first dose of OL-CZP in the SFE period, for subjects continuing into the SFE
- the later of Week 52 visit and last administration of OL-CZP or other treatment, for subjects who complete the 52 week main phase of the study and do not continue into the SFE
- the subject discontinues the study prior to the week 52 visit (WD visit) and does not fall into the above categories.

Subjects switching from double-blind treatment to OL-CZP treatment and then to OL-OT will have an OL-CZP and an OL-OT period.

Subjects continuing on the study with other treatment visits, but without taking other medication will be allocated to the OL-OT period although will not be considered as starting other treatment in that period. A medical review of all cases will be performed prior to the database lock to identify subjects with valid administration of other treatment. Start and end dates of identified other treatments will be taken from the concomitant medication page.

The use of open-label period data for efficacy is described in detail in the relevant efficacy sections in [Section 8](#). If applicable, open-label period data for efficacy will be mapped to the corresponding time-point post baseline for analysis. E.g. if a subject performs an open-label

Week 12 visit at 26 weeks post-baseline, corresponding efficacy data will be considered “week 26” assessments.

Open-label visit-based safety data (such as laboratory data and vital signs data) will in general be summarized and listed as separate visits from the double-blind period visits. However, open-label visits will still be presented by the double-blind treatment groups of CZP 200mg Q2W and placebo. In general, OL-OT safety data will not be presented in tables, but only listed.

For subjects who receive OL-CZP, data will be presented by the OL-CZP visits. Safety summaries which are summarized ‘At any visit’, ‘post-Baseline’ (including minimum or maximum post-Baseline) or ‘On treatment’ will be presented separately for each period (double-blind and OL-CZP). Visit based efficacy or safety data that is recorded on the day of first administration of OL-CZP or OL-OT will be assigned to the previous period unless available time information clearly indicates that it was recorded after the first administration of OL-CZP or OL-OT.

Concomitant medications will be assigned to all periods (double-blind, OL-CZP, OL-OT or SFE) according to the rules given in [Section 6.4](#).

AEs will be assigned to a period based on whether the AE started during the double-blind, OL-CZP, OL-OT period or SFE period. See [Section 11.2](#) for more detail.

All data reported will be listed.

#### **3.2.1.4 Follow-up period**

For subjects not entering the SFE period (no SFE informed consent), the Follow-up period will start after the later of Week 52 visit or last study medication administration (for subjects having Week 52 visit on double-blind or open-label therapy) or after the WD visit. Visit based efficacy or safety data that is recorded at the Week 52 or WD visit will be assigned to the previous period.

The Follow-up period will end on the Follow-up visit date. The Follow-up visit will take place 10 weeks after the last dose of study medication, which should be 8 weeks after the Week 52 visit (if the Week 52 is the last non-Follow-up visit) or less than 10 weeks after the WD visit (if the WD visit is the last non-Follow-up visit).

#### **3.2.1.5 Pre-SFE period**

The pre-SFE period starts after last dose of the double-blind period (i.e. also accounts for the last OL dose if the subject escaped) + 70 days (note that the last double-blind dose is at Week 50, thus each AE which starts up to 70 days after the last double-blind dose is still assigned to the double-blind phase) and ends before SFE period starts. The first SFE dose is used to determine if AEs end before the SFE period starts since this is the time when the AEs become treatment-emergent.

#### **3.2.1.6 SFE period**

The SFE period starts when the subject takes their first dose of OL-CZP that is after week 50 and after date of informed consent for the SFE. Visit based efficacy or safety data that is recorded on the day of the first SFE period dose will be assigned to the previous period unless available time information clearly indicates that it was recorded after the first administration of SFE period treatment. There are some subjects who took their first dose of OL-CZP that is after week 50

before the informed consent for the SFE. In such cases the SFE period will be programmed to start at the informed consent date.

The SFE period ends when the subject discontinues from or completes the study following SFE enrollment (Week 156/SFE-WD).

### 3.2.2 Relative day

The relative day will be included in the listings and will be calculated as follows:

- If the start (stop) date occurred on or after the first dose, and on or prior to the double-blind drug stop date, relative day is calculated as start (stop) date minus first double-blind dose date + 1. Relative day will be prefixed by a 'd' in the listings to show it's relative to double-blind treatment.
- For subjects not entering the OL-CZP period (including SFE period), if the start (stop) date occurred after the last dose of double-blind drug, the relative day to the most recent double-blind dose is calculated as start (stop) date minus most recent double-blind dose date. The relative day in this situation should be preceded by a 'd+'.
- For subjects entering the OL-CZP period (including SFE period), if the start (stop) date occurred on or after the first OL-CZP start date, and on or prior to the OL-CZP stop date (including SFE period), relative day is calculated as start (stop) date minus first open-label dose date + 1. The relative day in this situation should be preceded by a 'o'.
- For subjects entering the OL-CZP period (including SFE period), if the start (stop) date occurred after the last dose of OL-CZP drug, the relative day to the most recent OL-CZP dose is calculated as start (stop) date minus most recent OL-CZP dose date. The relative day in this situation should be preceded by a 'o+'.
- If the start (stop) date occurred before the first dose, the relative day is calculated as start (stop) date minus first dose date. The relative day in this situation should be preceded by a 'd-'.

For AEs, relative days for start and stop dates will be calculated as the number of days since the first injection of the relevant double-blind or OL-CZP medication. For non-treatment emergent AEs, relative day of onset will be negative if the event started and stopped before the first dose.

### 3.3 Definition of Baseline values

Unless otherwise specified, the last valid measurement before study medication administration in the double-blind period will be used as the Baseline value. The same Baseline definition will be used for the open-label period and SFE period. For almost all variables, this will be the assessment made at the Baseline visit. However, for some variables (eg, demography) assessments are scheduled for the Screening visit only and not for the Baseline visit. In this case, the Screening value will be utilized as Baseline value. If a Baseline visit measurement is missing, and a Screening visit measurement is available, the Screening value will be utilized as Baseline. If a scheduled Baseline assessment is taken on the same day as first administration of study medication and no time is collected, it will be assumed to have been taken prior to study medication.

Baseline images, either spinal x-ray or MRI assessments, are required to evaluate study eligibility. Therefore, all Baseline images will be available prior to randomization into the study. SI joint x-rays should not be older than 12 months prior to Baseline and should be verified by central reading during the Screening period.

There will be an additional SFE Baseline presented in some tables. It is defined as the last value before the patient received SFE treatment (the first dose on or after SFE informed consent, for most patients this will be the Week 52 value).

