## 10.2 Subject classification

Subjects will receive an overall classification, inclusive of Baseline and Post-Baseline results, and be classified as follows based on the ADAb assay results:

- ADAb negative: no confirmed positive ADAb samples at any of the sampling time points
- ADAb positive: confirmed positive ADAb samples at one or more sampling time points
- Missing: relevant samples are missing

Subjects baseline classification will be based on the ADAb assay test results at baseline

- Pre-ADAb negative: negative ADAb baseline sample
- Pre-ADAb positive: confirmed positive ADAb baseline sample
- Missing: no baseline ADAb sample

Baseline is defined as the sample immediately prior to or on the same day as first treatment with CZP. For subjects randomized to CZP, baseline will be Week 0 of the randomized treatment period and for subjects who were randomized to placebo but then received OL-CZP, baseline will be Week 0 of escape OL-CZP.

Subjects will receive a treatment-emergent classification based on the combination of the post-baseline ADAb assay results as well as the baseline ADAb sample result

- Treatment emergent ADAb negative: (i) subjects with no confirmed positive ADAb samples at any of the sampling time points, (ii) pre-ADAb positive subjects with all post baseline samples either ADAb negative or confirmed positive ADAb but with a titre below a pre-defined fold increase from the Baseline value (the fold increase from Baseline required to meet these criteria will be defined with the development of the assay and will be included in the TFLs)
- Treatment emergent ADAb positive: (i) pre-ADAb negative subjects with one or more confirmed positive samples post baseline, (ii) pre-ADAb positive subjects with one or more confirmed positive ADAb sample post baseline with a titre above a pre-defined fold increase from the Baseline value (the fold increase from Baseline required to meet these

criteria will be the same as that defined for treatment emergent ADAb negative and will be included in the TFLs)

- Missing: relevant samples are missing

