### 11.3 Clinical laboratory evaluations

The changes from Baseline in laboratory evaluations will be analyzed over time for the SS. In addition, last value (end of treatment), minimum value during treatment, and maximum value during treatment will be analyzed by period (double-blind and OL-CZP). End of treatment will be defined as last visit not including the Follow-up visit. During treatment for the minimum and maximum calculation will also exclude the Follow-up visit.

Shift tables concerning the normal range at end of treatment, minimum and maximum shift at any time will also be produced for each hematology and biochemistry laboratory parameter. The shifts will be categorized using L, N, H, missing, and total.

The number and percent of subjects with markedly abnormal ( $\geq$ grade 3 by RCTC) hematology or biochemistry values will be summarized at Any Visit, On Treatment (excluding the Follow-up visit) and by visit separately by period (double-blind or OL-CZP). Subject numbers for subjects with any markedly abnormal hematology or biochemistry value will be tabulated. Values fulfilling the criteria below will be classified as marked abnormal high (MH) or marked abnormal low (ML). If no lower (upper) limit is given, the classification ML (MH) is not applicable.

- Hemoglobin < LLN and decrease from Baseline >2g/dL
- Hemoglobin <8g/dL
- White blood cells <2000/ $\mu$ L
- Lymphocyte count <1000/ $\mu$ L
- Neutrophil count <1000/ $\mu$ L
- Platelet count <50000/ $\mu$ L
- ALT >3x upper limit normal (ULN)
- AST >3x ULN
- ALP >3x ULN
- Bilirubin  $\geq$ 2x ULN
- Creatinine >1.8x ULN
- Calcium >12.5mg/dL

- Calcium <7mg/dL
- CK >4x ULN
- Glucose >250mg/dL
- Glucose <40mg/dL
- Potassium >6.4mmol/L
- Potassium <3mmol/L
- Sodium <125mmol/L
- Uric acid  $\geq$ 3x ULN

The liver function test elevations will be displayed in an incidence table for the entire double-blind treatment period (including the Follow-up visit) and separately for the OL-CZP treatment period. A shift table will also be presented for double-blind and OL-CZP periods separately showing the change from baseline to maximum post-baseline category ( $\leq$ 1xULN, >1-<2xULN, 2-<3xULN and  $\geq$ 3xULN).

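### For placebo subjects who switch to open-label CZP, the Baseline-dependent laboratory and vital-sign tables for the OL-CZP period mix change on placebo with change on CZP

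*SAP*

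**What the plan says.** Section 3.3 of the SAP sets the general rule that, unless otherwise specified, "the last valid measurement before study medication administration in the double-blind period will be used as the Baseline value". It then extends the rule: "The same Baseline definition will be used for the open-label period and SFE period". The only other reference point in that section concerns the extension: "There will be an additional SFE Baseline presented in some tables". It is taken before SFE treatment, so it does not serve OL-CZP data collected before Week 52.

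Section 11.3 analyzes laboratory change from Baseline over time and the last, minimum and maximum values by period, OL-CZP included. It adds normal-range shift tables and a liver table: "A shift table will also be presented for double-blind and OL-CZP periods separately showing the change from baseline to maximum post-baseline category". One of its marked-abnormality criteria is "Hemoglobin < LLN and decrease from Baseline >2g/dL". Section 11.4.1 treats vital signs in the same by-period way, and each of its limits for systolic pressure, diastolic pressure and pulse also requires a change of a set size. Neither section names another Baseline.

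For antibodies, section 10.2 departs from the rule: "for subjects who were randomized to placebo but then received OL-CZP, baseline will be Week 0 of escape OL-CZP". Table 11-1 assigns an adverse event to the double-blind or the OL-CZP period according to whether it began before or after OL-CZP started.

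**The concern.** A placebo subject's Week 0 value precedes all of that subject's time on placebo. When the subject later receives OL-CZP, a change measured from Week 0 is the sum of what happened on placebo and what happened on CZP, yet it is tabulated under the OL-CZP period. A hemoglobin fall or ALT rise that arose on placebo and persisted then counts as an OL-CZP change or shift. In the other direction, a rise on placebo can hide part of a later fall on CZP.

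The PBO->OL CZP subjects supply safety data from first exposure to CZP, and the natural question about them is what changed after CZP began. The displays can also disagree about one event: an ALT rise reported as an adverse event during placebo is a double-blind TEAE, while the same persisting rise appears as an OL-CZP shift in the laboratory table.

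**Working it through.** The SAP states no figure on this point, so there is none to reproduce. The check has three parts.

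**1. Reference point by type of data, for a placebo subject who switches to OL-CZP**

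| Data | SAP section | Reference point |
|---|---|---|
| Laboratory change and shifts | 3.3, 11.3 | Week 0, before placebo |
| Vital-sign change | 3.3, 11.4.1 | Week 0, before placebo |
| Antibodies | 10.2 | Week 0 of escape OL-CZP |
| Adverse events | Table 11-1 | Start of OL-CZP |

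**2. Which criteria use Baseline**

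Section 11.3 lists 20 marked-abnormality criteria. Exactly one, the hemoglobin fall, refers to Baseline. The other 19 are absolute limits or ULN multiples and give the same result under any Baseline. The liver-elevation incidence table does not use Baseline either. What depends on Baseline is:
- the change-from-Baseline summaries, including those for last, minimum and maximum values;
- the normal-range and liver shift tables;
- the one hemoglobin criterion;
- the three vital-sign parameters in section 11.4.1.

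**3. The SAP's rules applied to one subject**

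The values are assumed; the rules are the SAP's. Change = OL-CZP value minus Baseline value.

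| Measure (rule) | Week 0 | Before first OL-CZP dose | On OL-CZP | Against Week 0 | Against pre-switch value |
|---|---|---|---|---|---|
| Hemoglobin, g/dL (below LLN, assumed 12, and fall >2) | 13.5 | 11.6 | 11.4 | 11.4 − 13.5 = −2.1, flagged | 11.4 − 11.6 = −0.2, not flagged |
| Systolic BP, mmHg (≤90 and fall ≥20) | 115 | 92 | 90 | 90 − 115 = −25, flagged | 90 − 92 = −2, not flagged |
| ALT, × ULN (liver shift categories) | 0.8 | 2.2 | 2.1 | ≤1 to 2-<3, a shift | 2-<3 to 2-<3, no shift |

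In each row nearly all of the change arose on placebo. All three OL-CZP findings disappear when the reference is the value before the first CZP dose.

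**Can a frequency be given?** Not from the SAP. A simulation of the hemoglobin criterion with no CZP effect shows why. It assumes mean 13.5 g/dL, between-subject SD 1.0, LLN 12, visit noise SD 0.4, drift SD 0.5 to 0.9 before the switch, and five OL-CZP visits.
- If drift stops at the switch: 0.8–4.8% flagged against Week 0, about 0.04% against the pre-switch value.
- If drift continues as a random walk, adding the same SD again over the OL-CZP visits: 1.9–10% against Week 0, 0.5–3.3% against the pre-switch value.

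The direction is the same in both cases. At drift SD 0.5 the ratio moves from about 20 (0.8/0.04) to about 4 (1.9/0.5) with one untestable assumption, so neither result should be cited as the size of the problem.

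**The case against.** The strongest defence is that this is a stated choice. Section 3.3 names the open-label period, and one study Baseline keeps double-blind and open-label changes on one scale. Antibody status is a natural exception, because treatment-emergent positivity needs a pre-CZP sample. This has weight: the Week 0 display is legitimate and should stay. It does not answer the first-exposure question for placebo switchers, and the SAP offers no display that does.

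The defence can add that the mixing is visible. Section 3.2.1.3 says "open-label visits will still be presented by the double-blind treatment groups of CZP 200mg Q2W and placebo", so switchers have their own column. That section also keeps minimum, maximum and any-visit summaries separate by period, so only a change still present at an OL-CZP visit carries over. By-visit tables show actual values beside changes (section 3.1), and all data are listed. These features help a reader detect the effect, but they do not remove it from the change, shift and flag tables.

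A switch-time Baseline has weaknesses too. The SAP does not say whether laboratory samples are taken at the switch, and after Week 12 the scheduled double-blind laboratory visits are Weeks 24, 36 and 52, so a fallback value may be some 12 weeks old or more. Investigators may stop treatment in non-responders (section 8.1.3.2), so the switch value is a selected one and open to some regression to the mean. These points stand. They argue for adding the second Baseline, not for replacing the first.

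A reader might infer more: that most OL-CZP marked abnormalities in switchers are placebo artefacts, or that the hemoglobin flag is inflated twentyfold or more. The documents support neither. Nineteen of the 20 criteria ignore Baseline, and a contrast that large requires hemoglobin drift to stop at the switch.

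**Conclusion.** The concern holds in a limited form. For PBO->OL CZP subjects, the Baseline-dependent OL-CZP laboratory and vital-sign tables measure change since before placebo, not change since CZP began. That is out of line with the SAP's own handling of antibodies and adverse events in the same subjects. The Week 0 rule is not an arithmetic error, and the adverse event tables and the primary efficacy analysis are unaffected.

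The bias can run either way, and it reaches only changes that persist into an OL-CZP visit. Its size depends on how many placebo subjects switch and how far their values drift before and after, none of which the SAP gives. The three-row example shows that the rules can produce the effect; it does not show how often they will. The point deserves correction because the remedy is cheap and removes nothing.

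**What to change.** In section 3.3, define a second Baseline for subjects randomized to placebo who receive OL-CZP: the last valid value before the first OL-CZP dose. Values recorded on the day of that dose can follow section 3.2.1.3, which assigns them to the previous period unless time information shows otherwise. In sections 11.3 and 11.4.1, present the following against this Baseline, for the PBO->OL CZP column:
- change-from-Baseline summaries;
- normal-range and liver shift tables;
- the hemoglobin-fall criterion;
- the blood pressure and pulse criteria.

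Keep the Week 0 display beside it, and keep Week 0 as the Baseline for CZP->OL CZP subjects. State how many switchers have a value at the switch and how old the fallback value is for the rest.

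The cost is one derived flag and one extra set of tables. No new data are needed: sections 4.2.2, 10.2 and 11.4.3.2 all refer to a Week 0 open-label visit, and the last earlier value serves where no sample was taken. The price is an older reference for some subjects and some regression to the mean at the switch. Week 52 outputs already exist (section 8.1.1), so the new tables should be labelled as added after that lock. Section 4.3 already has laboratory tables rerun at the final lock; the vital-sign tables would have to be added to that list.
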